**9.1.5. Early Termination Visit**

Subjects who are withdrawn from the study will be asked to provide final blood samples for drug concentration and immunogenicity analysis.

**9.1.6. Unscheduled Visits**

All attempts should be made to keep subjects on the study schedule. Unscheduled visits may be necessary to repeat testing following abnormal laboratory results, for follow-up of AEs, for SARS-CoV-2 RT-qPCR and serology testing when subjects experience symptoms consistent with SARS-CoV-2 infection (per the broad-term list specified in Section 9.2.2.2), or for any other reason, as warranted.

## 9.2. Study Procedures

This section describes the procedures and collections that will be performed in this study. Procedures and collections will occur according to the schedule of events ([Table 3](#) and [Table 4](#)).

### 9.2.1. Procedures Performed Only at the Screening/Baseline Visit

The following procedures will be performed for the sole purpose of determining study eligibility or characterizing the baseline population: demographics (eg, age, sex, race, weight, height, etc), medical history, local diagnostic assay for SARS-CoV-2, query for risk factors for SARS-CoV-2 infection (eg, first responder or healthcare worker; presence in outdoor or indoor crowded or public places [without keeping distance >6 feet] in the last 14 days, with or without a mask and/or eye protection; attendance to any social events with more than 10 people in the last 14 days, with or without a mask and/or eye protection; exposure to someone believed to have COVID-19; exposure to someone diagnosed with COVID-19; receipt of influenza vaccine as of July 2020), and household assessment in which subjects will be asked to provide general information about the household members (including their general demographic information, COVID-19 status, their risk of exposure to COVID-19, and treatment with an EUA approved monoclonal antibody treatment for COVID-19).

#### 9.2.1.1. Informed Consent

Informed consent (adults and parents/guardians) and pediatric assent must be obtained according to the requirements described in Section [13.2](#). Optional informed consent may be obtained for participation in the pharmacogenomics sub-study (refer to Section [9.2.7](#) for more information on this sub-study or inclusion in the R10933-10987-COV-2067 study).

#### 9.2.1.2. Local Diagnostic Assay for SARS-CoV-2

The investigator or sub-investigator will verify that the subjects tests negative or positive by a local diagnostic assay for SARS-CoV-2 (eg, molecular assay such as RT-PCR assay for SARS-CoV-2 or a SARS-CoV-2 antigen test using an appropriate sample such as NP, nasal, OP, or saliva). The local diagnostic assay for SARS-CoV-2 must be considered acceptable for clinical use by local standards. If the test has not been approved or received EUA issued by the US FDA or by the equivalent local health authority, then the Sponsor should be consulted. The use of a RT-PCR assay is highly recommended.

The local diagnostic test result, specimen type (eg, nasal swab), assay type, and date of test will be recorded in the CRF. The sample type collected is dependent on local lab requirements.

### 9.2.2. Efficacy Procedures

#### 9.2.2.1. Nasopharyngeal Swab SARS-CoV-2 RT-qPCR Test (Central Lab)

Nasopharyngeal swab sample will be collected from subjects to determine presence or absence of SARS-CoV-2 virus and to determine the relative quantification of viral load. For adult and adolescent subjects ( $\geq 12$  years of age), NP swab samples will be collected by swabbing through both nostrils on all planned timepoints ([Table 3](#)). For pediatric subjects ( $< 12$  years of age), NP swab samples will be collected by swabbing through a single nostril on all planned timepoints

([Table 5](#)). Detailed instructions for sample collections are in the laboratory manual provided to study sites.

### 9.2.2.2. COVID-19 Symptomology (Strict Terms, Broad Terms, and CDC Definition)

During each scheduled or unscheduled visit/contact, the investigator or sub-PI investigator, or designee (ie, nurse practitioner in countries where allowed by local law) will query the subject and/or subject's parent or guardian about adverse events the subject is experiencing or has experienced since the last visit/contact (eg, within the prior week if it is a weekly scheduled visit) and ask about all of the signs and symptoms associated with these adverse events including the start date, end date and severity of each. The investigator should avoid querying the subject and/or subject's parent or guardian by running a check-list of signs and symptoms, but rather allow the subject and/or subject's parent or guardian to spontaneously report everything that they presented.

All signs and symptoms related to the AEs, along with the corresponding start date, end date and severity should be documented in the subject's medical records (source document). As signs and symptoms may appear and resolve on different days and may precede or occur after the collection of NP swab sample for the SARS-CoV-2 RT-qPCR test, it is important that this detailed information be captured in the source document.

Independent of the results (positive or negative) of the SARS-CoV-2 RT-qPCR tests performed on samples collected from study subjects during the weekly or unscheduled visits, all adverse events must be documented in the AE CRF. Signs and symptoms related to the adverse events reported in the AE CRF and confirmed to be temporally related to a positive SARS-CoV-2 RT-qPCR test collected from the subject's NP swab sample will be reported on a separate CRF (individual sign or symptom with start date and end date, and associated severity).

For the purpose of the study's primary and secondary objectives, the assessment of association of symptomatic disease with SARS-CoV-2 infection (ie, diagnosis of strict term COVID-19, broad term COVID-19, and CDC definition of COVID-19) will be based on the strict term, broad term, and CDC COVID-19 definitions described below ([Table 7](#)) and the temporal relationship of the signs and symptoms with lab confirmed SARS-CoV-2 infection (based on central lab RT-qPCR test result).

### Temporal Relationship of Signs and Symptoms with Positive RT-qPCR for Diagnosis of COVID-19

The onset date of signs/symptoms will utilize a  $\pm 14$  days window from the date of the positive SARS-CoV-2 RT-qPCR, so long as the signs/symptom onset does not precede a negative SARS-CoV-2 RT-qPCR test. That is, the onset date of symptomatic SARS-CoV-2 infection is defined as the date of the first sign/symptom that is consistent with a diagnosis of COVID-19 as determined by the investigator. The onset date must be after the last negative SARS-CoV-2 RT-qPCR and no more than 14 days prior to the first positive SARS-CoV-2 RT-qPCR or must occur on or before 14 days after the last positive SARS-CoV-2 RT-qPCR.

### Definitions of COVID-19 Signs and Symptoms used for the Secondary Efficacy Endpoints:

1. **Strict term:** as described in Section [4.1.2](#) and Section [4.2.2](#), a secondary endpoint will utilize a strict definition of signs and symptoms of COVID-19 (see [Table 7](#)).

2. **Broad term:** as described in Section 4.1.2 and Section 4.2.2, a secondary endpoint will utilize a broad term COVID-19 signs and symptoms defined as any of the 23 symptoms listed in Table 7 or fever ( $\geq 38^{\circ}\text{C}$ ).
3. **CDC definition:** as described in Section 4.1.2 and Section 4.2.2, a secondary endpoint will utilize the CDC COVID-19 2020 Interim Case Definition (approved 5 Aug 2020) (see Table 7) to allow for comparability across studies in the field (CDC, 2020a).

**Table 7: Strict-Terms, Broad-Terms, and CDC Definition COVID-19 Signs and Symptoms**

Strict-term defined by:	Broad-term defined as any of the following:	CDC definition

Fever (<math>\geq 38^{\circ}\text{C}</math>) PLUS <math>\geq 1</math> respiratory symptom (sore throat, cough, shortness of breath)
 
OR
 
2 respiratory symptoms (sore throat, cough, shortness of breath)
 
OR
 
1 respiratory symptom (sore throat, cough, shortness of breath) PLUS <math>\geq 2</math> non-respiratory symptoms (chills, nausea, vomiting, diarrhea, headache, conjunctivitis, myalgia, arthralgia, loss of taste or smell, fatigue or general malaise)
	
Fever <math>\geq 38^{\circ}\text{C}</math>
 
 
• The signs and symptoms below:           
 
1. Feverish
 
2. Sore throat
 
3. Cough
 
4. Shortness of breath/difficulty breathing (nasal flaring*)
 
5. Chills
 
6. Nausea
 
7. Vomiting
 
8. Diarrhea
 
9. Headache
 
10. Red or watery eyes (conjunctivitis)
 
11. Body aches such as muscle pain or joint pain (myalgia, arthralgia)
 
12. Loss of taste/smell
 
13. Fatigue (fatigue or general malaise or lethargy*)
 
14. Loss of appetite or poor eating/feeding
 
15. Confusion
 
16. Dizziness
 
17. Pressure/tightness in chest
 
18. Chest pain
 
19. Stomach ache (abdominal pain*)
 
20. Rash
 
21. Sneezing
 
22. Runny nose
 
23. Sputum/phlegm
 
Other
 
 
 
	
At least 2 of the following symptoms: fever (measured or subjective), chills, rigors, myalgia, headache, sore throat, nausea or vomiting, diarrhea, fatigue, congestion or runny nose
 
OR
 
Any 1 of the following symptoms: cough, shortness of breath, difficulty breathing, new olfactory disorder, new taste disorder
 
OR
 
Severe respiratory illness with at least 1 of the following, clinical or radiographic evidence of pneumonia, ARDS.

*\*Signs and symptoms observed in pediatric subjects*

### 9.2.2.3. Assessment of Medically Attended Visits

Only for RT-qPCR positive subjects (cohort A, cohort A1, cohort B, and cohort B1): Subjects and/or their parent/guardian (as appropriate) who are or become SARS-CoV-2 RT-PCR positive will be queried on any SARS-CoV-2 infection-related medically attended visits to the ED, UCC, or hospitalization (Table 3 and Table 5). The assessment of medically attended visits to ED, UCC or hospitalization will be performed from the time the subject first becomes SARS-CoV-2 RT-qPCR positive or from the time they develop symptoms suspected to be COVID-19 (later confirmed by RT-qPCR positive results) until the subject has had 2 negative tests or COVID-19 related symptoms have resolved (whichever lasts longer), or until the end of study visit. Details associated with any SARS-CoV-2 infection-related medically-attended visit will be recorded and will include at minimum:

- Nature of the visit (ED, UCC, hospital stay)
- Date and length of visit
- Primary reason for the visit should be recorded as an adverse event
- Assessment of the following parameters or occurrences (worst or most abnormal finding) during the medically attended visit/stay:
  - Abnormal vital signs: respiratory rate  $\geq 30$  per minute, heart rate  $\geq 125$  per minute, peripheral capillary oxygen saturation ( $\text{SpO}_2$ )  $\leq 93\%$  on room air at sea level, or oxygen partial pressure ( $\text{PaO}_2$ )/fractional inspired oxygen ( $\text{FiO}_2$ )  $< 300$  mm Hg)  
*Note: these limits for abnormal vital signs are for adult and adolescent subjects.*
  - Respiratory failure: needing high-flow oxygen, noninvasive ventilation, mechanical ventilation, extracorporeal membrane oxygenation (ECMO)
  - Evidence of shock: systolic blood pressure (SBP)  $< 90$  mm Hg, diastolic blood pressure (DBP)  $< 60$  mm Hg, or requiring vasopressors  
*Note: these limits for abnormal vital signs are for adult and adolescent subjects.*
  - Multiorgan dysfunction: Significant acute renal, hepatic, or neurologic dysfunction
  - Multisystem inflammatory syndrome in children (MIS-C)  
*Note: for pediatric subjects  $< 18$  years only*
  - Admission to an ICU

### 9.2.2.4. Absenteeism Assessment

Only for RT-qPCR positive subjects (cohort A, cohort A1, cohort B, and cohort B1): Subjects and/or their parent/guardian who are or become SARS-CoV-2 RT-PCR positive during the EAP will be queried on any SARS-CoV-2 infection-related absenteeism (Table 3 and Table 5). Absenteeism is defined as number of days missed for daily responsibilities, including work (employed adults) or school (students), daycare, or family obligations/responsibilities (childcare or eldercare). The assessment of absenteeism will be performed from the timepoint the subject first becomes SARS-CoV-2 RT-qPCR positive until the end until the subject has had 2 negative tests or COVID-19 related symptoms have resolved (whichever lasts longer), or until the end of study visit.

### 9.2.3. Safety Procedures

#### 9.2.3.1. Targeted Physical Examination and Vital Signs

The targeted physical examination and vital signs include measurements of temperature, blood pressure (measured after the subject has been resting quietly for at least 5 minutes and may be obtained from a seated or supine position), pulse rate, and respiratory rate, and examination of the oropharynx, skin, heart, lungs and any other system(s) depending on any complaints or concerns expressed by the subjects.

Vital signs consisting of blood pressure, pulse rate, body temperature, and respiratory rate will be collected pre-dose and after dose administration as follows:

- **Sentinel group (subset 1; completed):** approximately every 30 minutes during the first 2 hours after study drug administration, at hour 3, and at hour 4 before dismissal.
- **Safety group (subset 2; completed):** approximately every hour for 2 hours after study drug administration.
- **All other adult and adolescent subjects (subset 3):** approximately 1 hour after study drug administration.
- **Pediatric sentinel group (subset 4):** approximately every hour for at least 2 hours after study drug administration (blood pressure will be measured, if feasible, according to the child's age).
- **All other pediatric subjects (subset 5):** approximately 1 hour after study drug administration (blood pressure will be measured, if feasible, according to the child's age).

#### 9.2.3.2. Laboratory Testing

Samples for laboratory testing will be collected at visits according to the Schedule of Events [Table 4](#) and [Table 6](#). Samples will be analyzed by a central laboratory. For pediatric subjects (<18 years) only, a numbing cream may be used for blood sample collection. Detailed instructions for blood sample collection are in the laboratory manual provided to study sites.

Tests will include:

### **Blood Chemistry**

Sodium	Total protein, serum	Total bilirubin
Potassium	Creatinine	Total cholesterol
Chloride	Blood urea nitrogen (BUN)	Triglycerides
Carbon dioxide	Aspartate aminotransferase (AST)	Uric acid
Calcium	Alanine aminotransferase (ALT)	Creatine phosphokinase (CPK)
Glucose	Alkaline phosphatase	
Albumin	Lactate dehydrogenase (LDH)	

### **Hematology**

Hemoglobin	Differential:
Hematocrit	Neutrophils
Red blood cells (RBCs)	Lymphocytes
White blood cells (WBCs)	Monocytes
Red cell indices	Basophils
Platelet count	Eosinophils

### **Urinalysis**

Color	Glucose	RBC
Clarity	Blood	Hyaline and other casts
pH	Bilirubin	Bacteria
Specific gravity	Leukocyte esterase	Epithelial cells
Ketones	Nitrite	Crystals
Protein	WBC	Yeast

### **Other Laboratory Tests**

Urine pregnancy test will be performed for WOCBP at baseline and prior to administration of study drug. If a subject has a positive urine pregnancy test, a serum pregnancy test should be performed to confirm.

### **Abnormal Laboratory Values and Laboratory Adverse Events**

All laboratory values must be reviewed by the investigator or authorized designee.

Significantly abnormal test results that occur after start of treatment **may** be repeated to confirm the nature and degree of the abnormality. When necessary, appropriate ancillary investigations should be initiated. If the abnormality fails to resolve or cannot be explained by events or conditions unrelated to the study medication or its administration, the Medical/Study Director must be consulted.

The clinical significance of an abnormal test value, within the context of the disease under study, must be determined by the investigator.

Criteria for reporting laboratory values as an AE are provided in Section 10.1.1.

### **9.2.4. Drug Concentration and Measurements**

Serum samples for REGN10933 and REGN10987 drug concentration measurement will be collected per the schedule of events for adult and adolescent subjects (Table 4) and pediatric subjects (<12 years of age) (Table 6). For pediatric subjects (<18 years) only, a numbing cream may be used for blood sample collection.

A subset of the first 30 adult subjects (by subject number by IVRS) will have frequent sample collection (dense PK). The second subset will include the next 370 adult subjects (the 31st to 400th subjects) who will have less frequent sample collection (sparse PK). Pediatric subjects will have 3 serum samples collected. In order to collect serum samples over the study duration, pediatric subjects will be assigned by IVRS to 1 of 4 sampling schedules (A, B, C, D) ([Table 6](#)). Any unused samples may be kept for up 15 years (or for a shorter time period if required per regional laws and regulations) after study completion for use in exploratory research.

### **9.2.5. Immunogenicity Measurements and Samples**

Immunogenicity will be assessed by ADA and NAb. Samples for ADA and NAb assessment will be collected for adult and adolescent subjects (<12 years) at time points listed in [Table 4](#). Samples will be assessed for ADA and NAb using samples collected for subjects (<12 years) at the time points listed in [Table 6](#), if feasible. For pediatric subjects (<18 years) only, a numbing cream may be used for blood sample collection. Any unused samples may be kept for up 15 years (or for a shorter time period if required per regional laws and regulations) after study completion for use in exploratory research.

### **9.2.6. Exploratory Pharmacodynamic/Biomarker Procedures**

A description of planned or potential exploratory analyses is provided below. Samples for assessment of pharmacodynamic and exploratory biomarkers will be collected from adult and adolescent subjects at time points indicated in [Table 4](#). Sample for serological assays will be collected from pediatric subjects (<12 years) at the time points indicated in [Table 6](#). For pediatric subjects (<18 years) only, a numbing cream may be used for blood sample collection. Residual serum or plasma samples collected for other purposes may also be used to study how REGN10933+REGN10987 work and SARS-CoV-2 infection, including but not limited to, cytokines, complement pathways, and other factors emerging to be associated with disease or clinical prognosis. Any unused samples may be kept for up 15 years (or for a shorter time period if required per regional laws and regulations) after study completion for use in exploratory research.

#### **9.2.6.1. Virology**

##### **9.2.6.1.1. Viral Sequencing**

In support of public health initiatives to track SARS-CoV-2 genetic variants, viral genome sequencing will be performed on all viral nucleic acid isolated from NP swab samples at baseline. Sequencing analyses will be of the entire viral genome, including the full gene sequence that encodes the SARS-CoV-2 S protein.

The results of the viral sequencing will not be included in the clinical study report.

##### **9.2.6.1.2. Viral Resistance**

Subjects will be assessed for virologic resistance, defined as (1) those subjects who are positive at baseline and remain positive without a consistent decrease in viral load by 4 weeks, (2) those subjects who were negative and become positive during the EAP, and/or (3) those subjects who have 2 consecutive negative RT-qPCR tests with a subsequent positive RT-qPCR test result. For

subjects who exhibit viral resistance, viral sequencing will be performed to understand the potential relationship between genetic mutations and mAb functional activity. Viral sequencing may also be done on a gender-matched placebo control group in order to determine whether any genetic mutations observed in the mAb treatment group are naturally emergent genetic variants.

The results of the viral resistance will not be included in the clinical study report.

#### **9.2.6.1.3. Viral Infectivity**

To explore the effects of REGN10933+REGN10987 on infectivity of SARS-CoV-2, we may use viral culture assays or sub genomic viral mRNA transcript analyses. Subgenomic viral RNA transcripts potentially indicate the presence of actively replicating virus in samples, as viral subgenomic mRNA is transcribed only in infected cells and is not packaged into virions. These data may be associated to RT-qPCR data from matched samples for each group and compare to placebo or other clinical or other measures in the study.

#### **9.2.6.2. Serological Assays for Endogenous Anti-SARS-CoV-2 Antibodies**

In order to assess the impact of baseline humoral immunity/antibody response to SARS-CoV-2 on REGN10933+REGN10987 efficacy to prevent SARS-CoV-2 infection, serum anti-SARS-CoV-2 will be measured at baseline, including but not limited to those which detect antibodies against the S protein and/or the N protein and/or neutralization assays. The impact of a positive serology result on drug efficacy will be assessed by associating seropositivity to positive SARS-CoV-2 RT-qPCR test from NP swabs. Association of seropositivity with clinical endpoints and other measures may also be explored.

To explore whether REGN10933+REGN10987 affect the generation of a humoral immune response to SARS-CoV-2, serum anti-SARS-CoV-2 N protein antibodies will be measured using immunoassays in REGN10933+REGN10987 groups as compared to placebo control, as well as to baseline.

Any unused samples may be kept for up 15 years after study completion for use in exploratory research (or for a shorter time period if required per regional laws and regulations).

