**Other Procedures:**

Drug Concentration and Immunogenicity measurements: Dense sample and sparse sample collection for drug concentration measurement will be performed in subsets of subjects. Samples for ADA and NAb assessment will be collected at various times throughout the study. Any unused serum samples may be used for exploratory research.

Serological Assays for Endogenous Anti-SARS-CoV-2 Antibodies: In order to assess the impact of baseline humoral immunity/antibody response to SARS-CoV-2 on REGN10933+REGN10987 efficacy to prevent SARS-CoV-2 infection, serum anti-SARS-CoV-2 will be measured at baseline, including but not limited to those which detect antibodies against the S protein and/or the N protein and/or neutralization assays. Samples will be collected from adult and pediatric subjects (<18 years).

Exploratory Pharmacodynamic/Biomarker and Serum/Plasma Samples for Research: Samples for assessment of pharmacodynamic and exploratory research will be collected from adult and adolescent subjects.

Pharmacogenomic Analysis (Optional): Adult and pediatric subjects (<18 years and >10 kg) subjects may participate in an optional genomics sub-study (separate informed consent required). Blood sample for RNA and DNA will be collected for this substudy.

---

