**Virologic efficacy:** The primary mechanism of action of REGN10933+REGN10987 is blockade of the S protein RBD interaction with ACE2, leading to inhibition of SARS-CoV-2 host cell infection. The ability of REGN10933+REGN10987 treatment to prevent SARS-CoV-2 infection will be evaluated by SARS-CoV-2 RT-qPCR test results from weekly NP swab samples. Weekly sample collection is considered an adequate collection frequency to ensure early detection of viral load (SARS-CoV-2 RT-qPCR positivity) in infected individuals; this is based on the average duration of viral positivity from NP swabs that ranges from 7 to 28 days (He, 2020) (Wölfel, 2020). All subjects will have SARS-CoV-2 RT-qPCR testing by NP sample. Nasopharyngeal swab testing has been shown to have good sensitivity and specificity for detecting SARS-CoV-2 RNA (Zou, 2020) (Pere, 2020). The administrative assessment of seronegative subjects (n=409) in cohort A demonstrated that the risk of becoming infected (ie, becoming SARS-CoV-2 RT-PCR positive) was reduced as early as the first week of study (10.3% in subjects in the placebo group versus 5.4% in subjects in the REGN10933+REGN10987 group at day 8). The protection continued through the following weeks. Both the magnitude and duration of infection were reduced by REGN10933+REGN10987 treatment. Infections occurring in subjects in the placebo group had, on average, more than 100-fold higher peak viral load. Infections in subjects in the REGN10933+REGN10987 group lasted no more than 1 week, while approximately 40% of infections in subjects in the placebo group lasted 3 to 4 weeks. No infected subjects in the REGN10933+REGN10987 group had high viral loads ( $>10^4$  copies/mL) compared to 62% of the infected subjects in the placebo group (13/21 placebo versus 0/9 REGN10933+REGN10987) (CDC, 2020b). (CDC, 2020b)

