#### 11.2.1. Cohort A: Adult and Adolescent Subjects ( $\geq 12$ years) Who Are SARS-CoV-2 RT-qPCR Negative at Baseline

In cohort A, subjects are randomized in a 1:1 allocation ratio to REGN10933+REGN10987 or placebo. The primary hypothesis is the reduction in the proportion of symptomatic RT-qPCR (broad-term) confirmed SARS-CoV-2 infections in seronegative subjects. To calculate the sample size required to achieve at least 90% power for seronegative subjects in cohort A, it is assumed that the statistical hypothesis will be tested in a 2-sided test. Based on the administrative assessment results among 409 seronegative subjects in cohort A, a 50% reduction of infections (symptomatic or asymptomatic) compared to the placebo group and a 100% reduction of symptomatic infections compared to placebo group was observed. Due to the small sample size in the administrative assessment, it is assumed, for the purpose of calculating study power, that an approximately 50% reduction or greater in symptomatic infections compared to placebo group will be expected for the final primary efficacy analysis.

In this household study design, the number of subjects per household, the correlation between subjects and symptomatic infection rates within a household are unknown. To detect a relative risk of 0.5 (ie, 50% reduction of the assumed 10% attack rate in the placebo arm), equivalent to an odds ratio of 0.47, power was calculated compared to the p-value of 0.05 based on 2000 simulations in 1248 subjects from 430 households (ie, assuming an average household size of 2.9 seronegative subjects). [Table 9](#) provides power calculations by varying degrees of correlation within household. In all cases, the power of the study is >90% using a generalized linear model with the generalized estimation equation (GEE) approach and assuming a compound symmetry covariance matrix.

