**Table 9: Simulated Power for Household Design (1248 Subjects over 430 Households)**

Placebo Attack Rate	REGN10933+REGN10987 Attack Rate	Correlation within Household	Average Odds Ratio REGN10933+REGN10987 versus Placebo	Power
10%	5%	0.1	0.485	0.914
10%	5%	0.2	0.485	0.934
10%	5%	0.3	0.480	0.956
10%	5%	0.4	0.481	0.972
10%	5%	0.5	0.476	0.983
10%	5%	0.6	0.478	0.999

At least 1980 subjects will need to be enrolled in cohort A to have a minimum of 1248 seronegative subjects, assuming that 10% of subjects drop out and 30% of subjects are seropositive at baseline.

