Proportion of subjects with negative RT-qPCR (based on central lab test) regardless of serology status at baseline who subsequently have a positive SARS-CoV-2 RT-qPCR and symptomatic (CDC definition) SARS-CoV-2 infection during the EAP	B
Proportion of baseline-seronegative or baseline-seropositive subjects with negative RT-qPCR (based on central lab test) who subsequently have a positive SARS-CoV-2 RT-qPCR and symptomatic (CDC definition) SARS-CoV-2 infection during the EAP	B
Proportion of baseline-seropositive subjects (based on central lab test) who subsequently have a positive SARS-CoV-2 RT-qPCR during the EAP	B
Time-weighted average of viral load (log10 copies/mL) from the first positive SARS-CoV-2 RT-qPCR in NP swab sample (that has an onset during the EAP) until third weekly visit after the first positive test in seropositive subjects (based on central lab test) during the EAP	C
Time-weighted average of viral load (log10 copies/mL) from the first positive SARS-CoV-2 RT-qPCR in NP swab sample (that has an onset during the EAP) until the second weekly visit after the first positive test in seropositive subjects (based on central lab test) during the EAP	C
Area under the curve (AUC) in viral load (log10 copies/mL) in NP swab samples from the first positive SARS-CoV-2 RT-qPCR NP swab sample until the first confirmed negative test, in seropositive subjects (based on central lab test) that has an onset during the EAP	C
Note: Only for RT-qPCR positive subjects during the EAP with confirmed negative tests in the seronegative mFAS	
Proportion of subjects in placebo group who have a RT-qPCR confirmed SARS-CoV-2 infection (regardless of symptoms) during the EAP by the status of household members participating in study R10933-10987-COV-2067 and receiving REGN10933+REGN10987 or whose household member did not receive treatment with REGN10933+REGN10987	B
Proportion of subjects who have a RT-qPCR confirmed SARS-CoV-2 infection (regardless of symptoms) during the EAP by the status of household members participating in study R10933-10987-COV-2067 and receiving REGN10933+REGN10987	B
Proportion of subjects who have a RT-qPCR confirmed SARS-CoV-2 infection (regardless of symptoms) during the EAP by the status of household members receiving an approved monoclonal antibody treatment for COVID-19	B

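### Protocol 9.2.6.2 assesses the effect of baseline serostatus on drug efficacy by associating serostatus with PCR positivity, which cannot separate efficacy from natural protection (minor, exploratory)

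*Protocol*

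**What the plan says.** The Synopsis (Other Procedures) and Protocol 9.2.6.2 give the same reason for measuring baseline antibodies: "In order to assess the impact of baseline humoral immunity/antibody response to SARS-CoV-2 on REGN10933+REGN10987 efficacy to prevent SARS-CoV-2 infection". Section 9.2.6.2 then supplies the method: "The impact of a positive serology result on drug efficacy will be assessed by associating seropositivity to positive SARS-CoV-2 RT-qPCR test from NP swabs". It mentions neither placebo nor treatment arm, and sets no test, population or alpha.

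Other parts of the plan do compare the arms by serostatus:

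- Protocol 2.1.4 and SAP 1.2.3 have an exploratory objective of drug against placebo in baseline-seropositive cohort A subjects.
- SAP 4.5.4 lists the matching endpoints, among them "Proportion of baseline-seropositive subjects (based on central lab test) who subsequently have a positive SARS-CoV-2 RT-qPCR during the EAP".
- SAP 5.7.4 analyses cohort A binary endpoints as the primary is analysed, by a GEE or logistic odds ratio between arms.
- PCR-confirmed infection in seronegatives is a key secondary endpoint (Protocol 4.1.2, SAP 5.7.3).

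No section compares the treatment effect between the two serostatus groups. Serostatus is in neither subgroup list (Protocol 11.4.3.1.2, SAP 5.7.1.2), the primary analysis set is seronegative only, and no interaction or heterogeneity test is named. SAP 1.2.4 reports no changes from protocol amendment 6.

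**The concern.** The stated question is one of effect modification: does the drug-versus-placebo contrast differ by baseline serostatus? The stated method relates serostatus to infection. Its null hypothesis is that serostatus is not prognostic, which is a different hypothesis.

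If prior antibodies protect, infection will be less common in seropositives in both arms, and the association will appear even when the drug works equally well in both groups. If instead the drug works in only one group, the overall infection rates by serostatus can coincide and the association will show nothing. Restricting to the drug arm does not help, because there is then no control. Only a comparison of the association between arms, which is the interaction, answers the question, and the text does not ask for it.

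About 30% of cohort A is expected to be seropositive, so an exploratory statement on this could easily be misread.

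**Working it through.** **Inputs from the documents**

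- Protocol 11.2.1 and Table 9: "At least 1980 subjects will need to be enrolled in cohort A to have a minimum of 1248 seronegative subjects". The allowances behind this figure are 10% for dropout and 30% for baseline seropositivity.
- Protocol 11.2.1: "subjects are randomized in a 1:1 allocation ratio to REGN10933+REGN10987 or placebo", and a "50% reduction of the assumed 10% attack rate in the placebo arm". The 10% and 5% rates are planning figures for symptomatic infection. They are used here as seronegative PCR infection rates. The administrative assessment in Protocol 3.2.6 is close to them: "10.3% in subjects in the placebo group versus 5.4% in subjects in the REGN10933+REGN10987 group at day 8".

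**Assumed:** the seropositive placebo risk, which the documents do not give (varied from 1% to 10%), and a two-sided 0.05 test, since 9.2.6.2 sets none. Household correlation is ignored.

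**Plan figures reproduced**

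- Seronegative: 1980 × 0.9 × 0.7 = 1247.4, against 1248 stated.
- Seropositive: 1980 × 0.9 × 0.3 = 534.6, so about 535.
- Odds ratio: (0.05/0.95)/(0.10/0.90) = 0.474.
- Power with 624 per arm, 10% v 5%, unclustered: 0.919, against 0.914 in the first row of Table 9.

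**Identical efficacy, worked for a 5% seropositive placebo risk**

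1. Seropositive drug-arm odds are (0.05/0.95) × 0.474 = 0.0249, a risk of 2.43%.
2. Pooled over arms, the risk is (5 + 2.43)/2 = 3.72% in seropositives and (10 + 5)/2 = 7.5% in seronegatives. The difference is 3.78 points, although efficacy is the same.
3. The null SE is √[0.0637 × 0.9363 × (1/1248 + 1/535)] = 0.0126. The alternative SE is √[0.075 × 0.925/1248 + 0.0372 × 0.9628/535] = 0.0111.
4. The rejection rate is Φ[(0.0378 − 1.96 × 0.0126)/0.0111], about 88%. Simulation (20,000 replicates) gives 89%.

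Simulated rejection rates under identical efficacy:

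| Seropositive placebo risk | Association, arms pooled | Association, drug arm only | Interaction (Breslow-Day) |
|---|---|---|---|
| 10% (no protection) | 4.8% | 4.8% | 4.9% |
| 8% | 20% | 9% | 5.1% |
| 5% | 89% | 41% | 4.9% |
| 3% | 99.9% | 78% | 4.8% |

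With no drug effect in either group and half the risk in seropositives, the pooled association still rejects 96% of the time.

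**Efficacy in seronegatives only (10% v 5%; seropositives 7.5% v 7.5%)**

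- The pooled risk is 7.5% in both groups, so the association has nothing to detect. It rejects 4.9%.
- The log odds ratio SE is √(1/62.4 + 1/561.6 + 1/31.2 + 1/592.8) = 0.227 in seronegatives and √[2 × (1/20.06 + 1/247.4)] = 0.328 in seropositives.
- The ratio of odds ratios is 1/0.474 = 2.11, with log SE √(0.227² + 0.328²) = 0.399. Then z = 0.747/0.399 = 1.87 and power is Φ(1.87 − 1.96), about 46%. Simulation gives 46% (Wald) and 47% (Breslow-Day).
- With seropositives at 5% v 5%, the drug-arm-only association rejects 5.1% and the interaction test about 39%.

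**At first-step size.** SAP 2.1 gives about 2459 subjects. Assuming 90% in cohort A and 30% of those seropositive gives 1549 and 664. The pooled association rejects 95% at half risk with identical efficacy. In the 7.5% v 7.5% case it rejects 5.2%, against 55% for the interaction test.

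**The case against.** The sentence sits among exploratory biomarker procedures, which Protocol 9.2.6 describes as planned or potential analyses. Section 11 is the basis for the SAP, and the SAP contains no test of serostatus against PCR. The pooled test above is therefore one way to carry out a loosely worded sentence. This stands as a reason for a low rating. It does not supply the missing contrast, because the sentence names both a question and a method, and the method does not answer the question.

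A reader might infer that efficacy in seropositive contacts goes unexamined, or that the trial would conclude that serostatus alters efficacy merely because seropositives are naturally protected. The documents do not support either. Treatment odds ratios on the same PCR endpoint are planned in both groups. In the seronegative-only scenario their expected values would be about 0.47 (95% CI 0.30 to 0.74) in seronegatives and 1.0 (0.53 to 1.90) in seropositives, so the pattern would be visible side by side. Nor is a positive association certain: it depends on a level of natural protection that the documents do not state.

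It is also fair to say that the plan uses no interaction test for any other subgroup, and that one here would have modest power. That argues for reporting an estimate with its interval, and against relying on a p-value.

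**Conclusion.** The point holds as a minor one. The association described in 9.2.6.2 cannot isolate efficacy, whether arms are pooled or the drug arm is used alone, and no other section contrasts the treatment effect between serostatus groups. At a nominal 0.05 it could suggest a difference in efficacy where none exists about 20% to over 99% of the time as seropositive placebo risk falls from 8% to 3%, and about 5% of the time without natural protection. It would miss a drug effect confined to seronegatives in the 7.5% v 7.5% case.

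These sizes rest on the planning attack rates, the assumed seropositive risk, a nominal test that the plan does not prescribe, and no household clustering. No primary, key secondary or alpha-controlled conclusion is affected.

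**What to change.** Replace the sentence in Protocol 9.2.6.2, or state it in the SAP, as follows:

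*The impact of baseline serostatus on drug efficacy will be explored in seronegative and seropositive cohort A subjects, excluding those in the administrative assessment, by adding serostatus and treatment-by-serostatus to the GEE/logistic model for RT-qPCR-confirmed infection during the EAP, reporting the ratio of odds ratios with 95% CI.*

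Report the association of serostatus with infection separately for each arm, labelled as prognostic. The exclusion matters: Protocol 11.4.9 keeps the 554 administrative-assessment subjects out of both efficacy analyses, and a model on all of cohort A would bring them back.

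The cost is one sentence and one exploratory model on data already collected. The estimate will be imprecise. With the planning numbers and no effect in seropositives at 7.5% risk, the expected ratio of 2.11 has a 95% CI of about 0.97 to 4.6 (2.11 × exp(±1.96 × 0.399)), and power is about 39% to 47% across the two no-effect scenarios. It should be read as an estimate with its CI, and a non-significant result should not be taken as evidence of equal efficacy.
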